that VK may intervene in glucose metabolism through other mechanisms not fully described, such as suppression of inflammation. Also, it has been reported that VK improves insulin sensitivity in peripheral tissues without intervening in insulin resistance. Rasekhi et al. analyzed the effects of administering 100 mcg of VK through supplements on glucose metabolism in premenopausal prediabetic women. They found that in the group with VK ingestion, OCc levels increased and OCuc levels decreased and insulin sensitivity showed to improve. There were no alterations in total osteocalcin or in the HOMA-IR index. Which suggests that VK could improve insulin action in peripheral tissues.

Dietary supplementation with VK has been associated with an increase in insulin sensitivity and improvement in glycemic status. Yoshida et al. studied vitamin K supplementation for 36 months in men and women, administering 500 mcg/day of VK, 600 mg of calcium in the form of calcium carbonate and 10 mcg of vitamin D. They found that VK in supplements produces a protective effect on the progression of insulin resistance; Hussein et al. showed in animal models with type 2 diabetes the effect on glycemic status after the administration of VK supplements for 8 weeks. Those rats type showed a decrease in fasting serum glucose, HbA1c and insulin resistance, in addition to improving insulin sensitivity. When comparing the control group with the diabetes group without supplements, total OC levels were lower in the diabetes group; however, there was a dose-dependent relationship and the group with VK supplements showed to increase OC levels. In Mexico, the numbers of obesity and overweight increase considerably, the dietary factor has high relevance in the generation of these conditions, currently, studies on vitamin supplementation have been carried out, however in our country there is no evidence of the effect of dietary intervention with a high intake of VK on people with metabolic disorders such as overweight and obesity, so carrying out this study may contribute to explaining the participation of a high intake of VK on the improvement and prevention of overweight and obesity, in addition to evaluating the possibility to improve metabolic and bone health from a diet calculated in the Mexican population.

Work hypothesis

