Dietary intervention with a high intake of vitamin K of 500mcg for 6 weeks, increases VK and OC serum levels, decreases insulin and leptin levels and reduces cardiovascular risk in young adults, with and without overweight or obesity.

Aims

General aim

To evaluate the effect of dietary intervention with a high intake of vitamin K of 500mcg on serum levels of vitamin K, insulin, osteocalcin, leptin and on cardiovascular risk in young adults with and without overweight or obesity.

Specific aims

- Design a dietary intervention with a 500mcg of vitamin K

- Compare serum levels of vitamin K, insulin, osteocalcin, leptin and cardiovascular risk markers before and after the intervention with high vitamin K intake in subjects with and without overweight or obesity.
- Analyze the relation between vitamin K serum levels and body composition characteristics, metabolic markers and insulin, osteocalcin, leptin and cardiovascular risk percentage in subjects with and without overweight or obesity.

Ethical considerations:

The study will adhere to the regulations established by the Mexican government in the regulations of the general health law regarding health research.

It will be carried out in accordance with the ethical standards and principles for medical research on human subjects established in the Declaration of Helsinki in Helsinki, Finland in 1964, updated in 2008 in Seoul, South Korea.

The subjects who will participate in the study will voluntarily sign the informed consent letter. The project aims to contribute to the study of metabolic diseases in adults and young people with the aim of finding strategies for prevention or use as early dietary treatment and the consideration of foods with a high supply of vitamin K. The participants in the study will be assigned an identification key to guarantee the reliability of their clinical data. If they decide to withdraw from the study, the clinical history and biological samples associated with the individual will be deleted. All individuals who participate in the study will benefit from obtaining and explaining their clinical data, information about the cardiovascular risk they have at the time of the intervention and after it, in addition to being provided with nutritional care and intervention by professionals of nutrition, all this without costs.

Biosafety aspects:

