2. Dietary intervention with a high intake of vitamin K for 6 weeks

- Weekly monitoring of dietary adherence
- Nutritional advice: resolve doubts, evaluation of dietary adherence.

3. Final evaluation

- Evaluation of nutritional status: anthropometric analysis.
- Blood sample collection: determination of glucose and serum lipids, vitamin K, insulin, osteocalcin and leptin.
- Blood pressure measurement.
- Final evaluation of dietary adherence through a survey.

4. Data analysis, statistics.

5. Results report

Statistical analysis:

The statistical analysis will be carried out with the statistical package SPSS version 20, GraphPad Prism 9 and Excel 2011. Initially, the Kolmogorov-Smirnov test will be applied to all variables to verify if they followed a normal distribution model. Those variables that followed a normal distribution will be analyzed using parametric tests; Otherwise, non-parametric statistics will be applied.

Descriptive Analysis: mean, standard deviation, standard error of the mean, minimum, maximum and range. Inferential Analysis: Parametric tests (Student's t for independent samples), non-parametric tests (Kruskal Wallis). Comparative analysis: Chi square. Correlations: Spearman for non-parametric and Pearson for parametric tests.

Probability values less than 0.05 will be considered significant.

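### The rationale looks to vitamin K itself, but everyone receives one dietary programme with no comparator, and 6-week change in weight or fat mass is neither a before-after outcome nor used in reading the insulin and cardiovascular results

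*Combined protocol and SAP*

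**What the plan says.** - **Aim and hypothesis:** the general aim is given as "To evaluate the effect of dietary intervention with a high intake of vitamin K of 500mcg on serum levels of vitamin K, insulin, osteocalcin, leptin", together with cardiovascular risk. The Work hypothesis says that the 6-week intervention "decreases insulin and leptin levels and reduces cardiovascular risk in young adults, with and without overweight or obesity". Both name a diet rather than an isolated nutrient.
- **Background:** the study "may contribute to explaining the participation of a high intake of VK on the improvement and prevention of overweight and obesity". Here the interest is in vitamin K intake itself.
- **Specific aims:** the second compares serum and cardiovascular risk markers "before and after the intervention with high vitamin K intake in subjects with and without overweight or obesity". Body weight and fat mass are not among the measures it lists. The third relates serum vitamin K to body composition and the other markers.
- **What participants receive:** dietary indications at the start (Research organization, item 1), then weekly adherence checks and nutritional advice (item 2). Ethical considerations also promises all of them "information about the cardiovascular risk they have at the time of the intervention and after it, in addition to being provided with nutritional care". Energy and macronutrient content are not given. Participants with and without overweight or obesity all receive the intervention, and no other arm is described.
- **Anthropometry:** item 1 names bioimpedance, skin folds and circumferences. Item 3 says only "Evaluation of nutritional status: anthropometric analysis". Weight is implied by the bioimpedance scale under Technical methods but is not named.
- **Blood panels:** leptin is in the final panel (item 3) but not in the initial one (item 1).
- **Statistical analysis:** independent-samples t test, Kruskal-Wallis, chi-square, and Pearson or Spearman correlation. No adjusted analysis is named.

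**The concern.** Advice from nutrition professionals with weekly contact can change how much people eat as well as how much vitamin K they eat. If participants lose fat over the 6 weeks, insulin, blood pressure and lipids may improve for that reason alone. The hypothesis would then appear confirmed, and a reader following the background would credit vitamin K.

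This is related to the missing control group but is not the same problem. A control arm without the programme would show whether the programme works, but not whether vitamin K or fat loss was responsible. The plan already holds one partial safeguard, anthropometry at both evaluations, and does not use it for this purpose. If fat loss were greater in participants with overweight or obesity, the result could also be misread as a vitamin K effect particular to that group.

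**Working it through.** The plan states no sample size, power, effect size or standard deviation, so there is no figure to reproduce. The point rests on reading sections together; the arithmetic only illustrates size.

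**Step 1. Can the plan separate vitamin K from weight change?**

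| Possible route | What the plan provides |
|---|---|
| Comparator with the same contact but without high vitamin K | None described |
| Rest of the diet fixed, or weight held stable | Not stated |
| Energy intake measured before and after | 24-hour recall at the initial evaluation only; an adherence survey at the end; content of the weekly checks not described |
| Weight or fat change as an outcome | Not in the hypothesis or specific aim 2 |
| Adjustment for weight or fat change | None named |
| Body composition in correlations | Yes, with serum vitamin K (specific aim 3) |

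The last route does not separate the effects. Participants who follow the diet closely may both raise their vitamin K and lose weight, so a bivariate correlation of serum vitamin K with insulin could reflect either.

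**Step 2. How often would a before-after test be significant with no vitamin K effect?**

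Assumptions, none from the documents: *n* participants in one before-after comparison; advice, contact and weight change together shift the marker by *d* standard deviations of the change score; two-sided 0.05. (The plan gives 0.05 without sidedness and names no paired test, so a paired comparison is also assumed.)

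P(significant) = Φ(d√n − 1.96) + Φ(−d√n − 1.96)

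For d = 0.3 and n = 40: 0.3 × 6.325 = 1.897, and Φ(1.897 − 1.96) = Φ(−0.063) = 0.475; the second term is negligible.

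| n | d = 0 | d = 0.2 | d = 0.3 | d = 0.5 |
|---|---|---|---|---|
| 20 | 5% | 14.5% | 26.9% | 60.9% |
| 30 | 5% | 19.5% | 37.6% | 78.2% |
| 40 | 5% | 24.4% | 47.5% | 88.5% |
| 60 | 5% | 34.1% | 64.2% | 97.2% |

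**Step 3. Would adjusting for weight change cure it?**

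Simulation, 2,000 runs per row: n = 40, vitamin K effect zero, total effect of everything else 0.4 SD, weight change with mean −0.8 and SD 1 in units of its own SD. The adjusted result is the intercept from regressing marker change on weight change, that is, the change expected at no weight change.

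| Share of the effect that runs through weight | Unadjusted, significant | Adjusted, significant | Mean adjusted change (SD) |
|---|---|---|---|
| All | 72% | 4% | 0.00 |
| Half | 70% | 17% | −0.20 |
| None | 69% | 48% | −0.40 |

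The Step 2 formula with d = 0.4 and n = 40 gives 0.4 × 6.325 = 2.530 and Φ(0.570) ≈ 72%, in line with the unadjusted column. Adjustment removes the part that runs through weight and leaves the rest, with vitamin K contributing nothing in any row.

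**The case against.** The strongest reply is that the general aim and hypothesis already name a dietary intervention, so a conclusion about the diet is what the protocol promises. This stands for the aim. The vitamin-K-specific reading comes from the background, which is worded tentatively, and from the third specific aim. The mismatch is therefore between rationale and aim; it is not an outright claim in the aim about 500 mcg of vitamin K alone.

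It can also be said that fat change is measured after the diet starts. If vitamin K itself affected body fat, as the background hopes, adjustment would remove part of a real effect. This stands too, and is why the adjusted analysis can only be supportive.

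A reader might infer more than the documents support:

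- *That the whole diet is redesigned or energy-restricted.* The text speaks of a calculated diet and dietary indications and gives no composition. The supportable point is that the rest of the diet is unspecified.
- *That participants learn their cardiovascular risk before the final blood draw and change their behaviour.* In "information about the cardiovascular risk they have at the time of the intervention and after it, in addition to being provided with nutritional care" the time phrase most naturally describes which risk is reported, not when it is disclosed. No disclosure schedule is given.
- *That body composition has no analytic role.* The third specific aim gives it one, though not one that separates these effects.
- *That a change surviving adjustment for fat mass would show a vitamin K effect.* Step 3 shows otherwise, and time trends and regression to the mean would remain as well.
- *That a leptin change can be computed and adjusted.* As listed, there is no baseline leptin.

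**Conclusion.** The concern holds in a limited form. Followed as written, the plan could credit vitamin K with a fall in insulin or cardiovascular markers produced by weight loss or by the rest of the programme, and no planned analysis would reveal it. The documents do not show that weight loss will occur or how large it would be.

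The size is therefore illustrative. With no vitamin K effect, 20 to 60 participants and other influences worth 0.2 to 0.5 SD, a before-after test would be significant in roughly 15% to 97% of studies. At 40 participants and 0.4 SD the figure is about 70%, and adjusting for weight change brings it to between 4% and 48%, depending on how much of the effect runs through weight. Only a comparator with the same advice and contact but without the high vitamin K content could isolate vitamin K. Short of that, reporting weight and fat change and limiting the conclusion is a worthwhile improvement.

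**What to change.** 1. Add 6-week change in body weight and fat mass to the before-after comparison in specific aim 2. State that the same bioimpedance measurement is made at both evaluations. Report these changes beside those in insulin and cardiovascular markers, separately for participants with and without overweight or obesity.
2. Report the marker changes unadjusted and, as a supportive analysis only, adjusted for change in fat mass. State that fat change is measured after the diet starts and may be a mediator, so that persistence after adjustment does not establish a vitamin K effect.
3. Word all conclusions as effects of the dietary programme, not of vitamin K alone, and align the rationale with this.
4. Reconcile the initial and final blood panels with specific aim 2 before planning any analysis of leptin change.

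**Cost:** some wording, a little more analysis and a more modest conclusion. No extra visit is needed, and no extra measurement if the final anthropometry already includes bioimpedance. Leptin is the exception: as listed, its baseline data are not collected. The adjusted estimate will usually be less precise. In the Step 3 setting its standard error is larger by a factor of about √(1 + 0.8²) = 1.28 when weight change explains none of the marker change.

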This is an investigation with minimal risk, the laboratory has the necessary infrastructure and materials for the management of RPBI according to the Official Mexican STANDARD NOM-087-ECOL-SSA1-2002, Environmental protection - Environmental health - Biological hazardous waste - infectious

- Classification and handling specifications. Waste from the use of reagents for ELISA and wet chemistry will be discarded according to the manufacturer's criteria. The reagents will be stored according to what is stipulated in the manufacturer's sheets and according to the provisions of NOM-054-SEMARNAT1993 and NOM-052-SEMARNAT-2005, no toxic, radioactive or explosive reagents will be worked with. The implementation of the project will be subject to what is described in the General Health Law on health research, DOF reform 04-02-2014 Art. 13 to 17. The main researcher has been trained by the CUCS Biosafety Committee.

METHODOLOGY

Technical methods and instruments for collection, recording, processing and analysis:

- Peripheral blood samples will be taken by venipuncture using the Vacutainer® system.
- The serum variables of glucose, triglycerides and lipids will be obtained by means of colorimetric enzymatic reagents. Vitamin K and insulin will be obtained through ELISA Kits.
- Anthropometric measurements will be carried out using a TANITA brand bioimpedance scale, SECA brand measuring tape and Slim Guide brand plicometers. All measurements will be taken according to ISAK.
- Blood pressure will be measured with an OMRON brand baumanometer.
- Patient data will be recorded in a log and in an Excel database. For the statistical processing of the data, the Excel, SPSS Statistics version 20.0 and GraphPad Prism 8 programs will be used.

Research organization:

The study will be carried out at the University of Guadalajara, Department of Molecular Biology and Genomics, Biochemistry Research Laboratory of the University Center for Health Sciences.

1. Once the patients are included, an initial evaluation will be carried out that consists of:

- Evaluation of nutritional status: Dietary analysis by 24-hour recall, anthropometric analysis (with bioimpedance, measurement of skin folds and circumferences), clinical history.
- Blood sample collection: determination of glucose and serum lipids, vitamin K, insulin and osteocalcin.
- Blood pressure measurement.
- Dietary intervention: Explanation of the study and dietary indications.

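### Leptin is hypothesised to fall and is to be compared before and after the diet, but the listed initial blood panel does not measure it

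*Combined protocol and SAP*

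**What the plan says.** The combined protocol and SAP refers to leptin as an outcome in four places before it reaches the visit schedule.

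- **Work hypothesis:** the diet "decreases insulin and leptin levels and reduces cardiovascular risk in young adults, with and without overweight or obesity".
- **General aim:** to evaluate the effect of the diet "on serum levels of vitamin K, insulin, osteocalcin, leptin and on cardiovascular risk in young adults".
- **Second specific aim:** "Compare serum levels of vitamin K, insulin, osteocalcin, leptin and cardiovascular risk markers before and after the intervention".
- **Third specific aim:** "Analyze the relation between vitamin K serum levels and body composition characteristics, metabolic markers and insulin, osteocalcin, leptin". No timepoint is given.

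The schedule under Research organization then gives two blood panels.

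- **Item 1, initial evaluation:** "Blood sample collection: determination of glucose and serum lipids, vitamin K, insulin and osteocalcin".
- **Item 3, final evaluation:** "Blood sample collection: determination of glucose and serum lipids, vitamin K, insulin, osteocalcin and leptin".

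Two other places bear on the point. The technical methods state that "Vitamin K and insulin will be obtained through ELISA Kits", and no method is named for leptin. The Statistical analysis section gives the inferential tests as Student's "t for independent samples), non-parametric tests (Kruskal Wallis", which are tests for independent groups. No control group is described.

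**The concern.** A claim that leptin falls needs a leptin value from before the diet, and the initial panel does not provide one. No later analysis can recover a baseline that was never measured, and there is no control group whose final values might stand in for it.

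One directional part of the hypothesis and the leptin part of the second specific aim therefore cannot be tested on the written schedule. What the listed tests could still do with leptin is compare final-visit levels between people with and without overweight or obesity. That comparison answers a different question, and a significant result could be misread as evidence about the diet.

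**Working it through.** **Step 1. Compare the two panels** (items 1 and 3 of Research organization, counting determinations as the panels list them).

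| Determination | Initial | Final |
|---|---|---|
| Glucose | yes | yes |
| Serum lipids | yes | yes |
| Vitamin K | yes | yes |
| Insulin | yes | yes |
| Osteocalcin | yes | yes |
| Leptin | no | yes |

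The initial panel has 5 determinations and the final panel 6. Leptin is the only difference. Of the four serum outcomes in the general aim (vitamin K, insulin, osteocalcin, leptin), 3 have both timepoints and 1 has the final visit only.

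**Step 2. Look for a baseline value elsewhere.** No other section schedules leptin at entry or plans a later assay of stored baseline serum. Both panel sentences are complete, so the difference does not look like lost or redacted text.

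**Step 3. See what the remaining comparison estimates.** Let *g* be the leptin gap between weight-status groups before the diet, and let *c* be a change common to both groups. Take the mean of the group without overweight or obesity as 0 at baseline.

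- Final-visit difference = (*g* + *c*) − (0 + *c*) = *g*. The common change drops out.
- If the changes differ (*c*₁ and *c*₂), the final-visit difference = *g* + (*c*₁ − *c*₂). Without baseline leptin the two parts cannot be separated.
- With baseline leptin, the within-person change in each group is (*g* + *c*₁) − *g* = *c*₁ and (0 + *c*₂) − 0 = *c*₂, which is what the second aim asks for.

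The hypothesis expects a fall in both groups, so a shared fall is a natural case.

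**Step 4. Illustrate the size.** The document gives no sample size and no leptin SD, so the group sizes and gaps here are assumptions. The 0.05 level is the plan's; two-sided testing is assumed. For a two-sample t test with SD 1 and *n* per group, the noncentrality is *g*√(*n*/2) on 2*n* − 2 degrees of freedom. For *n* = 30 and *g* = 0.5 this is 0.5 × √15 = 1.94 on 58 degrees of freedom. Rejection rates:

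| *n* per group | *g* = 0 | *g* = 0.5 SD | *g* = 1.0 SD |
|---|---|---|---|
| 15 | 0.05 | 0.26 | 0.75 |
| 30 | 0.05 | 0.48 | 0.97 |
| 50 | 0.05 | 0.70 | 0.999 |

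Each entry is the same whether the common fall is 0, 0.25, 0.5 or 1.0 SD, because *c* does not enter the noncentrality. A simulation of 20,000 runs at *n* = 30, with common falls of 0, 0.5 and 1.0 SD, gave 0.048, 0.052 and 0.049 for *g* = 0; 0.477, 0.479 and 0.477 for *g* = 0.5; and 0.967, 0.966 and 0.967 for *g* = 1.0.

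**Step 5. Mark what survives.** The third specific aim names no timepoint, so a vitamin K–leptin correlation at the final visit is still possible. Only its baseline and change-on-change versions are lost.

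**The case against.** The strongest reply is that this is a slip of the pen. The hypothesis, general aim and second specific aim treat leptin exactly like vitamin K, insulin and osteocalcin, and the protocol's lists are incomplete elsewhere: osteocalcin is in both panels yet also has no named assay. That reading is plausible. It does not remove the problem, because item 1 sets out what the initial evaluation comprises and laboratory staff will work from that list.

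A second reply is that the gap may be recoverable. The Ethical considerations section provides for disposing of a participant's biological samples on withdrawal, which suggests that samples are kept for some time. It does not establish that baseline serum is stored in a usable state or in sufficient quantity for leptin.

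Three narrower points stand as limits on the concern.

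- The rejection rates rest on assumed values and concern a test that the plan does not specifically prescribe for leptin. The inconsistency is textual and does not depend on them.
- Adding baseline leptin restores the before-after comparison, but without a control group a change still could not be firmly attributed to the diet.
- The listed tests include no paired test. That affects vitamin K, insulin and osteocalcin equally and is a separate matter.

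It can also be said that leptin is one of several outcomes and no primary outcome is named. That limits the damage to the leptin claims but does not make them testable.

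**Conclusion.** The concern holds, with high confidence, and must be fixed. The hypothesis and second specific aim require a leptin change that the listed schedule cannot produce. The loss is confined to leptin: one of the four serum outcomes in the general aim, one directional claim of the hypothesis, and the leptin part of the second aim. The final-visit correlation under the third aim remains available.

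This conclusion rests only on the text of the aims and the two panels. It assumes that the panels are followed as listed and that no unmentioned procedure supplies baseline leptin. That a shared fall cancels from the group comparison is algebra; only the illustrative rejection rates need assumed sample sizes and gaps.

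**What to change.** Reconcile the hypothesis and aims with items 1 and 3 of Research organization.

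1. **If baseline blood has not yet been drawn:** add leptin to the initial panel in item 1, using the draw already planned. In the technical methods, name one leptin assay to be used at both visits.
2. **If baseline blood has been drawn:** assay leptin in any retained baseline serum, by the same method as the final samples.
3. **If no baseline serum remains:** remove the leptin decrease from the hypothesis and leptin from the before-after comparison in the second aim. Limit the general aim's leptin component to final-visit associations, and state that the third aim's leptin correlation uses final-visit values.

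Record whichever route is taken in a dated amendment that gives the reason, so that any narrowing of the leptin claims is visible.

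The cost of the first route is one extra leptin determination per participant, one word in item 1 and one sentence naming the assay. This assumes that the planned draw yields enough serum. The exact laboratory cost cannot be given, because the protocol names no leptin assay.

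### The plan reports no before/after change with a confidence interval, and gives non-normal variables no median or quartiles

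*Combined protocol and SAP*

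**What the plan says.** The general aim begins "To evaluate the effect of dietary intervention with a high intake of vitamin K of 500mcg on serum levels" and goes on to several markers and cardiovascular risk. The second specific aim is to "Compare serum levels of vitamin K, insulin, osteocalcin, leptin and cardiovascular risk markers before and after the intervention". The work hypothesis gives directions: vitamin K and osteocalcin up; insulin, leptin and cardiovascular risk down.

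Under Statistical analysis, a Kolmogorov-Smirnov check decides the route: "Those variables that followed a normal distribution will be analyzed using parametric tests; Otherwise, non-parametric statistics will be applied". The planned outputs are then:

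- one descriptive list, not split by distribution: "Descriptive Analysis: mean, standard deviation, standard error of the mean, minimum, maximum and range";
- independent-samples t, Kruskal-Wallis and chi-square tests;
- correlations: "Correlations: Spearman for non-parametric and Pearson for parametric tests";
- one decision rule: "Probability values less than 0.05 will be considered significant".

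The section does not say whether the descriptive list applies to each visit, to each weight group or to changes. It mentions no change score, confidence interval, median or quartile.

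**The concern.** The aim is a within-person change, and the planned outputs do not include that change with its uncertainty. Two things are at stake.

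First, the documents give no sample size or power. If insulin comes out not significant, the reader cannot tell whether the change was small or there were too few people to see it. Only an interval for the change separates the two.

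Second, a variable that fails the normality check would be tested by ranks but tabulated by mean, SD, SEM and extremes. If it is skewed, the mean sits away from the typical value and the SD describes the spread poorly, so the table may not point the same way as the test.

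**Working it through.** The only number in the plan that bears on this point is the 0.05 threshold, so there is no stated figure to reproduce. The check is first a reading of the text, then an illustration on assumed values.

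**Aim against output.** The Specific aims require a before/after comparison in the same people. No named test is paired: the independent-samples t and Kruskal-Wallis tests both treat their samples as separate people. The correlations serve the third specific aim (relations between markers), not the change. No listed output carries the precision of the change.

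**Can the precision be recovered from visit summaries?** With SDs s1 and s2 at the two visits and before/after correlation r, the variance of the change is s1² + s2² − 2·r·s1·s2. The value of r is neither planned nor recoverable from the two SDs or SEMs. Assume equal SDs (set to 1) and n complete pairs. Then:

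- paired 95% half-width = t(0.975, n−1) × √(2(1−r)/n);
- half-width if the visits are treated as independent = t(0.975, 2n−2) × √(2/n).

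For n = 20 and r = 0.3: 2.093 × √(1.4/20) = 0.554. Treated as independent: 2.024 × √(2/20) = 0.640.

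| n (assumed) | r = 0.3 | r = 0.5 | r = 0.8 | as if independent |
|---|---|---|---|---|
| 20 | 0.554 | 0.468 | 0.296 | 0.640 |
| 30 | 0.442 | 0.373 | 0.236 | 0.517 |
| 40 | 0.378 | 0.320 | 0.202 | 0.445 |
| 60 | 0.306 | 0.258 | 0.163 | 0.362 |

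(Units: SD of the marker at one visit.) At n = 20, treating the visits as independent makes the interval 0.640/0.554 = 1.16 to 0.640/0.296 = 2.16 times too wide, depending on an r that the reader would not have.

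**What a non-significant verdict leaves open.** In units of the SD of the change, the half-width is t(0.975, n−1)/√n: 0.47, 0.37 and 0.32 for 20, 30 and 40 pairs. A two-sided paired t test has 80% power only for a true change of 0.66, 0.53 or 0.45 SD. For example, with 30 pairs an observed change of 0.30 SD gives 0.30 ± 0.37, that is −0.07 to 0.67: not significant, yet compatible with a moderate change.

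**Skewed variables.** Assume a log-normal marker with log-SD s. Relative to the median, the mean is exp(s²/2), the SD is the mean × √(exp(s²) − 1), and the quartiles are exp(±0.6745·s).

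| s (assumed) | mean | SD | mean − 2 SD | quartiles |
|---|---|---|---|---|
| 0.3 | 1.05 | 0.32 | 0.40 | 0.82, 1.22 |
| 0.5 | 1.13 | 0.60 | −0.08 | 0.71, 1.40 |
| 0.8 | 1.38 | 1.30 | −1.23 | 0.58, 1.72 |
| 1.0 | 1.65 | 2.16 | −2.67 | 0.51, 1.96 |

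From s = 0.5 upwards, mean minus 2 SD is negative for a quantity that cannot be negative. At s = 0.3 the harm is slight.

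**The case against.** The best defence is that the pieces of an estimate are already there. With complete pairs, the difference between the two visit means is the mean within-person change. A reader might infer that the trial will never estimate the size of the change, and that goes too far. The plan also does not say what the descriptive list is applied to; applied to change scores, mean and SEM would give the interval directly. What stands is that the plan is silent on this, names no paired test, and mentions no interval.

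A reader might also say that the plan misdescribes its non-normal variables. The documents give no distributions, so skewness is an assumption, and minimum, maximum and range are valid for skewed data. Nor is the case for the median that a rank test compares medians; in general Kruskal-Wallis does not. The case is only that median and quartiles describe a skewed variable better. Dropping SEM and range would be a matter of taste, and the point does not depend on it.

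Two further objections hold in full. Leptin appears in the blood sample list for the final evaluation but not in the list for the initial one (Research organization), so as written there is no leptin change to estimate. And no untreated comparison group is described, so even a correct interval would not isolate the effect of the diet.

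**Conclusion.** The point stands as a reporting and analysis gap that should be closed. Followed as written, the plan leaves the before/after change without a valid measure of precision, and gives non-normal variables no measures of centre and spread other than mean, SD, SEM and the extremes.

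The size can only be illustrated. At 20 pairs, the half-width of the change runs from 0.30 to 0.55 SD as the correlation falls from 0.8 to 0.3, and visit summaries alone would suggest 0.64 SD. For a log-normal marker with log-SD 0.3 to 1.0, the mean exceeds the median by 5% to 65%. The sample sizes, correlations, equal SDs and log-SDs are all assumptions. That no interval, paired analysis, median or quartile is planned rests on the text alone.

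**What to change.** In the Statistical analysis section:

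- For each hypothesised outcome measured at both visits, report the within-person change with a 95% CI, overall and by weight group. Use the mean paired change when the changes are roughly symmetric, and the geometric mean ratio (log scale) or the Hodges-Lehmann estimate when they are skewed.
- Let this paired analysis replace the independent-samples test for the before/after comparison.
- Interpret non-significant results from the interval, not from p<0.05 alone.
- Add median and quartiles for every variable analysed non-parametrically.
- Reconcile the initial and final blood sample lists for leptin before any leptin change is planned.
- Present the intervals as change over six weeks, not as the causal effect of the diet.

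The cost is a few sentences in the plan and some extra table columns. No new data are needed for outcomes listed at both visits; for leptin that cannot be said until the two lists agree.
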